6.1 Estimation of sample size

A total of 378 subjects are proposed to be enrolled in this clinical trial. This study is a non-inferiority design with parallel control. The equivalent products already available on the market (BD Pre-filled Flush Syringes) are selected as the control group device. The study intends to investigate that the overall performance of the investigational device group device for flushing and/or locking the catheter is non-inferior to that of the control group device. According to previous clinical experience, the overall performance success rate of equivalent devices for flushing and/or locking catheters is about 98%. Hence, it is assumed that the treatment completion rate of the investigational device group is consistent with that of the equivalent device. This study adopts a non-inferiority design, with α =0.025 (one-sided), β =0.1 (power of test of 90%), and the non-inferiority margin of 5%. The subjects in the investigational device group and the control group are allocated in an equal ratio of 1:1. The sample size shall be calculated to each enroll 165 subjects into the investigational device group and the control group by using the PASS software. However, 368 subjects shall be included to participate in this clinical study considering factors such as drop-out of subjects (drop-out rate of 10%) during the trial and other factors.

This study will be performed by 63 authorized nurses who participate in using the study device, each nurse will randomly use 3 investigational devices and 3 control devices, so a total of 378 subjects will be proposed to be enrolled in this clinical trial.

Minimum and maximum number of subjects and reasons for each clinical trial institution

This trial will be conducted simultaneously in multiple clinical trial institutions to enroll subjects. In principle, the subjects enrolled at each site will be distributed as evenly as possible to ensure adequate site representation. However, given the feasibility and enrollment progress, the number of subjects enrolled at each site will be properly adjusted according to the actual situation, so as to ensure the relative balance of the enrollment size of each site, and the final enrollment size of a particular site shall not exceed 50% of the total number of cases, and at least not less than half of the number of cases borne by the average distribution.

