3.2 Study population and sample size

The study population includes subjects who require locking and flushing the end of catheter line at the intervals of different drug treatment. Specific inclusion and exclusion criteria are described in the 5.2 Selection of subjects of Protocol.

A total of 378 subjects are proposed to be enrolled in this clinical trial. The study is a parallel-controlled, noninferiority design in which the control device is the BD Pre-filled Flush Syringes, a kind of prevalent product already on the market. The study intends to investigate the overall performance of the test device for flushing and/or locking the catheter that shall be non-inferior to that of the control device. Based on previous clinical experience, the overall performance pass rate of control device for flushing and/or locking the catheter is about 98%, and the study assumes the same treatment completion rate for the test device and control device. This study adopts a non-inferiority design, with α =0.025 (one-sided), β =0.1 (power of 90%), and the non-inferiority margin is 5%. The test group and the control group are allocated 1:1 in equal proportions. The sample size shall be calculated by using the PASS software and 165 subjects shall be enrolled into each of the test group and the control group. However, 368 subjects shall be included in this clinical study considering factors such as dropouts (drop-out rate of 10%) during the trial and other factors.

This study will be performed by 63 authorized nurses who participate in using the investigational device, each nurse will randomly use 3 test devices and 3 control devices, so a total of 378 subjects are proposed to be enrolled in this clinical trial.

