For the primary effectiveness indicator, i.e., overall performance of catheter flushing and/or locking, intergroup comparisons are performed using the Breslow-Day test for parity of effectiveness across sites. The Breslow-Day test is not required if the rate is 100% for both groups in each site, and the effectiveness is considered not statistically different between sites.

A Breslow-Day test with a P > 0.05 means that there is no statistical difference between sites, and the effectiveness data of each site can be combined for analysis. For the difference in the pass rate of the pre-filled flush syringes used to flush and/or lock the catheter in the combined test and control device groups, the 95% confidence interval (CI) for the difference in the pass rate between the two groups is calculated using the Wald method.

A Breslow-Day test with a $P \le 0.05$ indicates a statistical difference between sites, and that the effectiveness data may not be combined for analysis and need to be statistically described separately for each site. Point estimates corrected for site factors are obtained by weighting the difference in the pass rate of the pre-filled flush syringes used to flush and/or lock the catheter by the minimal risk method^[1] for the test device group and the control device group in each site, and the 95% confidence interval (CI) for the difference in the pass rate between the two groups is calculated using the Wald method.

If the pass rate is 100% in both groups, the Newcombe Wilson method ^[2] is used to calculate the 95% confidence interval (CI) for the difference in the pass rate between the two groups.

If the results show that the lower limit of the bilateral 95% confidence interval (CI) for the difference in the pass rate between the test device group and the control device group for pre-filled flush syringes used to flush and/or lock the catheter is greater than -5% (a pre-defined non-inferiority limit), H_0 is rejected and the test device group can be considered non-inferior to the control device group in terms of overall performance pass rate.

The procedure code for calculating confidence interval (CI) about the site-adjusted CMH rate difference is shown below:

/*Variable description: dataset is the input dataset, siteid represents the study site, nurseid represents the nurse, trtp represents the treatment factor, y represents the outcome variable*/

data dataset;

set dataset;

if group="test group" then trt=1;else trt=2;

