/*group is the group variable in the analyzed dataset, and "test group" is generally the value of the group variable, which represents the investigational test device*/

if main="pass" then var=1;else var=2;

/*main is the analyzed variable, and "pass" is generally the dichotomous value of the main variable, which represents the study effect */

run; ods select print; ods output CrossTabFreqs=CrossTabFreqs; proc freq data=dataset; table siteid*trt*var.*Generate a four-cell table; run: quit; proc sort data = dataset; by siteid trt; run; ods select print; ods output BinomialCLs=BinomialCLs; proc freq data=a; by siteid trt; table var/bin(cl=wilson level="1");*Wilson confidence interval is generated in preparation for newcombe method; run; quit; /******Calculate site-adjusted CMH rate difference by using the minimum risk method*** ****************************** proc sql undo policy=none; create table n11 as

select distinct siteid, Frequency as n11

```
from CrossTabFreqs where trt=1 and var=1;
quit;
proc sql undo policy=none;
  create table n12 as
    select distinct siteid, Frequency as n12
    from CrossTabFreqs where trt=1 and var=2;
  ;
quit;
proc sql undo policy=none;
  create table n21 as
     select distinct siteid, Frequency as n21
    from CrossTabFreqs where trt=2 and var=1;
quit;
proc sql undo policy=none;
  create table n22 as
     select distinct siteid, Frequency as n22
    from CrossTabFreqs where trt=2 and var=2;
quit;
data n1234;
  merge n11 n12 n21 n22;*Generate the number of four cells in a four-cell table;
  p1=n11/sum(n11,n12);p2=n21/sum(n21,n22);*Calculate the pass rates of test and control groups: p1,p2;
  p1 p2=p1-p2;
  n=sum(n11,n12,n21,n22);
  diffn=p1 p2*n;
  var=p1*(1-p1)/sum(n11,n12)+p2*(1-p2)/sum(n21,n22); *The variance of the rate difference;
  if var=0 then var 1=1;else var 1=1/var;
 ***If both groups of studies are analyzed at 100%, the variance of the rate difference is 0 and the inverse of
the variance is set to 1:
  dvar 1=p1 p2*var 1;
run;
proc sql undo_policy=none;
  create table riskdiff0 as
    select *,sum(n) as s n,sum(diffn) as s diffn,
        sum(var 1) as s var 1,sum(dvar 1) as s dvar 1
    from n1234;
quit;
data riskdiff;
  set riskdiff0;
  alaph=diffn*s var 1-s dvar 1;
  beta=var 1*(1+alaph*s diffn/s n);
run;
proc sql undo policy=none;
  create table riskdiff as
     select *, sum(alaph*dvar 1) as s advar 1,
        sum(beta*p1_p2) as s_betadif
    from riskdiff;
quit;
data riskdiff;
  set riskdiff:

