  w_diff=beta/s_var_1-(alaph*var_1/(s_var_1+s_advar_1))*(s_betadif/s_var_1);***Calculate the weights
  for rate difference in each site by the minimal risk method;
run;
proc sql undo policy=none;
  create table a riskdiff as
     select *,sum(p1 p2*w diff) as a riskdiff
```

from riskdiff:

```
quit;**Perform weighted estimation of the rate difference between the two groups in each site;
/*****Calculate the confidence interval of rate difference by using Newcombe
                                                                                        and Wald
                               ****
method**
data BinomialCLs1 BinomialCLs2;
  set BinomialCLs;
  if trt=1 then output BinomialCLs1;
  if trt=2 then output BinomialCLs2;
run;
data newcombe0;
merge a riskdiff
BinomialCLs1(keep=siteid LowerCL uppercl
              rename=(LowerCL=LowerCL1 uppercl=uppercl1))
BinomialCLs2(keep=siteid LowerCL uppercl
              rename=(LowerCL=LowerCL2 uppercl=uppercl2));
run;
proc sql undo policy=none;
  create table newcombe as
    select *,sum(LowerCL1*(1-LowerCL1)*w diff**2/sum(n11,n12)) as part1,
          sum(uppercl2*(1-uppercl2)*w_diff**2/sum(n21,n22)) as part2,
          sum(LowerCL2*(1-LowerCL2)*w diff**2/sum(n21,n22)) as part3,
          sum(uppercl1*(1-uppercl1)*w diff**2/sum(n11,n12)) as part4,
          sum(w diff*var) as part
    from newcombe0
quit;* Calculate the prepared parts of the formula by using newcombe and wald methods;
data newcombe wald:
  set newcombe;
  a newcombe l=a riskdiff-probit(1-0.025)*sqrt(part1+part2);
  a newcombe u=a riskdiff+probit(1-0.025)*sqrt(part3+part4):
  a wald l=a riskdiff-probit(1-0.025)*sqrt(part);
  a wald u=a riskdiff+probit(1-0.025)*sqrt(part);
run;*Substitute into the formula;
```

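### The SAP code for the site-adjusted Wald interval omits the square on the weights and builds weights that need not sum to 1, so in that branch non-inferiority can be missed through a coding error

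*SAP*

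**What the plan says.** SAP 6.3.1 first tests homogeneity across sites with Breslow-Day. If P > 0.05, the sites are pooled and a simple Wald interval is used. If P ≤ 0.05, the text reads: "Point estimates corrected for site factors are obtained by weighting the difference in the pass rate", using the minimal risk method, again with a Wald 95% interval. If both groups have a 100% pass rate, a Newcombe-Wilson interval is used. Non-inferiority is declared when the lower limit exceeds -5%.

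The SAP then prints code for the site-adjusted interval (some underscores were lost when the PDF was read). For each site it takes the rate difference `p1_p2`, its variance `var`, and `diffn`, which is the difference times the site size. Three lines matter here:

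- the weight term: "alaph=diffn*s var 1-s dvar 1"
- the Wald variance: "sum(w diff*var) as part"
- the decisive limit: "a wald l=a riskdiff-probit(1-0.025)*sqrt(part"

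The four Newcombe terms, in the same SQL step as the Wald variance, multiply by `w_diff**2`.

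**The concern.** Two lines do not do what the method text asks.

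1. The adjusted estimate is the sum of weight times site difference. Its variance is the sum of squared weight times site variance. The Wald line leaves out the square.
2. The weight term subtracts a sum built on plain differences from a term built on differences multiplied by site size. The two parts are on different scales, so the weights need not sum to 1 and the estimate need not be a weighted average of the site differences.

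This is prespecified code for the primary endpoint. In the P ≤ 0.05 branch its limit decides the trial, and text and code give different answers. If that is found after the data are seen, choosing between them becomes a post hoc decision on the primary analysis.

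**Working it through.** **Inputs from the documents.** Pass rate 98% in both arms, margin 5%, one-sided alpha 0.025, power 90%, 378 subjects at 1:1 (189 per arm), three sites (SAP 3.1 to 3.3). These reproduce the plan's sample size: (1.960 + 1.282)² × 2 × 0.98 × 0.02 / 0.05² = 164.8, so 165 per group; 165/0.9 gives 184 per group, 368 in total.

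**Assumptions.** The documents give no site-level counts. I use 63/63/63 and 94/63/32 per arm. The second split respects Protocol 6.1, under which "the final enrollment size of a particular site shall not exceed 50% of the total number of cases" (188/378 = 49.7%) and the smallest site needs at least half the average (64 subjects against 126/2 = 63). Failure counts are illustrative.

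**The square.** Write d for a site's difference, V for its variance and S = Σ(1/V). With inverse-variance weights w = (1/V)/S and three sites:

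- as coded: Σ wV = 3/S
- correct: Σ w²V = 1/S
- half-width ratio: √3 = 1.73

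**The weights.** In the coded algebra the weights sum to 1 whenever Σ(alaph/V) = 0.

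- With alaph = d·S − Σ(d/V), this sum is S·Σ(d/V) − S·Σ(d/V) = 0, so the weights always sum to 1.
- With `diffn` = n·d in place of d, it is S·Σ((n − 1)·d/V), which is generally not 0, even with equal sites.

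**Example A in full.** 63 per arm per site; failures test 2/0/3, control 0/1/0 (97.4% v 99.5%); Breslow-Day P = 0.0495.

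- d: -3.17, +1.59, -4.76 points. V: 4.879, 2.480, 7.199 (×10⁻⁴). 1/V: 2049.6, 4033.0, 1389.2.
- Σ(d/V) = -65.07 + 64.02 − 66.15 = -67.20. This is not 0, so the coded weights cannot be relied on to sum to 1.
- As coded: weights 0.401/0.414/0.315, sum 1.13; estimate -2.115%; Σ wV = 5.250×10⁻⁴; half-width 1.96 × √(5.250×10⁻⁴) = 4.491%; lower limit -6.61%.
- Both lines corrected: weights 0.360/0.356/0.285, sum 1 before rounding; estimate -1.933%; Σ w²V = 1.528×10⁻⁴; half-width 2.423%; lower limit -4.36%.
- Half-width ratio 4.491/2.423 = 1.85.

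**All three examples, lower limit against -5%**

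| Example | Per arm by site | Failures, test / control | Breslow-Day P | Coded weight sum | As coded | Square only | Both fixes |
|---|---|---|---|---|---|---|---|
| A | 63/63/63 | 2,0,3 / 0,1,0 | 0.0495 | 1.13 | -6.61% | -4.83% | -4.36% |
| B | 63/63/63 | 0,1,4 / 4,1,0 | 0.016 | 1.00 | -5.28% | -3.05% | -3.05% |
| C | 94/63/32 | 0,1,6 / 4,1,0 | 0.005 | 0.70 | -6.38% | -3.47% | -4.04% |

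Each example fails as coded and passes when corrected. In C the corrected weights (0.3727/0.4970/0.1304) agree to four decimals with a direct solution that minimises variance plus squared bias subject to weights summing to 1. The coded weights are 0.1640/0.4453/0.0936.

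**Simulation at 98%/98%, 200,000 trials per row**

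| Per arm by site | Branch entered | Non-inferior in branch, coded v corrected | Lost, of all trials |
|---|---|---|---|
| 63/63/63 | 4.6% | 54% v 94% | 1.8% |
| 94/63/32 | 4.2% | 60% v 90% | 1.2% |
| 55/55/55 | 4.3% | 46% v 89% | 1.8% |

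With 63 per arm per site, overall power is 90.2% as coded and 92.0% corrected. The median half-width ratio is 1.74 (5th to 95th percentile 1.67 to 1.87) when every site has a failure, and 1.42 (1.37 to 1.53) when one has none. With 94/63/32, a second simulation gave a median of 1.69 (1.36 to 1.81). Coded weight sums ran from 0.88 to 1.15 with equal sites and 0.74 to 1.16 with 94/63/32 (5th to 95th percentile). Where Breslow-Day could not be computed (2% to 8% of trials), the pooled path was assumed.

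**The case against.** The strongest reply is that the fault is conservative and rarely reached. Under homogeneous 98% rates the branch is entered in under 5% of trials, coded power stays at the 90% target with 63 per arm per site, and the sponsor bears the cost. That stands, and it limits the weight of the point.

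The two faults are also unequal. The square causes nearly all the widening, and correcting it alone restores a pass in all three examples. The weight fault can act either way: square-only is too favourable in C and too severe in A. Example B cannot test the weights, because its overall difference is zero and both versions coincide. This stands too. The weight fault shifts the estimate and the limit but reverses no decision here.

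The SAP defines minimal risk only through its reference 1, so the intended objective function is an inference. But weights summing to 0.70 cannot be an average of site differences under any objective, and the code alone shows this.

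Loss of the square in PDF reading is unlikely, since the exponent survives in the four neighbouring terms. The code also looks unfinished: it reads a dataset `a` that is never created. A test run might expose that, but an interval that is merely too wide raises no error message.

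Finally, the corrected formula is less protective. At 93% v 98%, false non-inferiority within the branch was about 0.3% as coded, against about 5% (equal sites) or 4% (94/63/32) corrected. So a missed claim is missed relative to the method the SAP specifies, not relative to a limit that holds 2.5%.

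**Conclusion.** The concern holds. As written, the code does not produce the minimal-risk Wald limit that the text of SAP 6.3.1 prescribes. In the Breslow-Day P ≤ 0.05 branch the half-width is too wide by a factor of about 1.4 to 1.9. That is a central range; single simulated trials ran from about 1.1 to 2.0. The primary conclusion can reverse.

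The consequence is lost power: 1.2% to 1.8% of all trials at 98%/98%, and more if sites truly differ, because the branch is then entered more often. Across 1,000,000 simulated trials in five scenarios, the coded version never claimed non-inferiority where the corrected one did not. The pooled path and the 100%/100% Newcombe path are unaffected.

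The faults follow from the code alone; their size rests on the assumed site splits, failure counts and true rates. Correction does not cure a separate feature of the plan. At a true difference of -5 points, overall false non-inferiority is 3.7% as coded and 3.9% corrected with equal sites, and 3.8% and 4.0% with 94/63/32, all above 2.5%. The code should be corrected before the data are analysed.

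**What to change.** In the SAP 6.3.1 code:

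1. Replace the Wald variance with `sum(w_diff**2*var) as part`.
2. Replace the weight term with `alaph=p1_p2*s_var_1-s_dvar_1`.
3. Add a check that `w_diff` sums to 1 over sites, and run the program on a test dataset with unequal sites and a non-zero overall difference.

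Make the first two changes together, since correcting only the square leaves the limit off in either direction. The cost is two edited lines, one check and a test run. The method text and the Wald decision rule do not change.

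Two further steps are optional design choices, not corrections. One is to reconsider setting the inverse variance to 1 for a site with 100% in both arms, which gives that site almost no weight. The other is to report the Newcombe limits that the code already computes as a sensitivity analysis.

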6.3.2 Secondary effectiveness evaluation

```
(1)
        Evaluation Indicators
```

- Criteria for overall performance of catheter flushing and/or locking; 1)
- Ease of pushing of the plunger during catheter flushing and/or locking 2)
- Evaluation method (2)

FAS and PPS are used for evaluation.

Calculate the criteria for overall performance of catheter flushing and/or locking, as well as the number and percentage of cases in each category for ease of pushing of the plunger (including a score of \geq 3) during flushing or locking. A chi-square test/Fisher's exact probability method is used for inter-group comparison on the criteria for overall performance of catheter flushing and/or locking, as well as for the scores of ≥ 3 for ease of pushing of the plunger during flushing or locking. The rank correlation rank sum test is used to compare between groups for the ease of pushing of the plunger during flushing or locking.

6.4 Safety evaluation

(1) Evaluation Indicators

Adverse events and serious adverse events

(2) Evaluation method

Safety analysis is conducted based on safety set (SS).

The Medical Dictionary For Regulatory Activities (MedDRA) version 25.1 is used for adverse event coding. Adverse events that occur prior to the start of the flush syringe treatment are only shown in the list.

Adverse events that occur not earlier than the use of investigational device or that exist before the use of investigational device but get severe at or after the use of the investigational device are considered TEAEs. If multiple adverse events of the same preferred term (PT) occur in the same subject, the most serious one is used for the final intergroup comparison.

The number, frequency and proportion of TEAEs and investigational device-related TEAEs occurring in each group are tabulated and summarized according to system organ classification (SOC), preferred term (PT) and severity. If the same adverse event occurs multiple times in the same subject, the most serious one is used for analysis.

Severe TEAEs, TEAEs leading to study discontinuation, and TEAEs leading to death are summarized for each group by system organ classification (SOC) and preferred term (PT), respectively.

Adverse events related to the investigational device include those judged as "definitely related, likely related, and probably related" in relation to the investigational device.

Adverse events leading to study discontinuation (including whether the adverse event leads to withdrawal from the trial) are judged as "yes".

Adverse events leading to death (including prognosis) are selected as "Death".

All adverse events during the study are detailed in the list.

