12.1.2 Classification of adverse event

Mild: The adverse event is tolerable, does not affect the diagnosis and treatment, does not require special treatment, and has no impact on the subject's health.

Moderate: The adverse event is intolerable, requires special treatment, and has a direct impact on the subject's health.

Severe: The adverse event endangers the subject's life, causing death or disability, and immediate emergency treatment is required.

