12.1.4 Observation and recording of adverse events

The investigator shall collect and record the adverse events from each subject during the period from the signing of informed consent form to the termination of follow-up. Any adverse event, regardless of its severity, or whether it is related to the medical device, is required to be recorded and described on the adverse event form for study medical records. Investigators need to determine the date of occurrence, severity, whether to take corresponding measures, and to judge the correlation between the adverse events and the medical devices.

The subject undergoing such adverse events shall be followed up until the adverse events are recovered (return to normal state or to baseline state), or until the condition is stable, or until a reasonable explanation is available.

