7.2 Missing of severity of adverse events

The severity of adverse events prior to flush syringe treatment is missing and is filled using "moderate". Missing of severity of adverse events occurring after the start of flush syringe treatment is filled using "severe" and these filled-in values are used for summary of occurrence rate only and are presented as original values in the final list.

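### SAP 6.4 counts a pre-existing adverse event as treatment-emergent only if it gets severe; read against the protocol's grades, this leaves mild-to-moderate worsening after the flush out of the TEAE tables

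*SAP*

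**What the plan says.** Protocol 12.1.4 collects adverse events "during the period from the signing of informed consent form to the termination of follow-up", so an event can be on record before the syringe is used. SAP 6.4 then sorts events by timing. For those before treatment it says: "Adverse events that occur prior to the start of the flush syringe treatment are only shown in the list". An event is treatment-emergent if its onset is not earlier than device use. The only other route is for events "that exist before the use of investigational device but get severe at or after the use of the investigational device are considered TEAEs".

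The safety tables follow from that definition: "The number, frequency and proportion of TEAEs and investigational device-related TEAEs occurring in each group are tabulated and summarized", by system organ class, preferred term and severity.

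The severity scale is in Protocol 12.1.2. The lowest grade reads: "Mild: The adverse event is tolerable, does not affect the diagnosis and treatment, does not require special treatment". The middle grade, Moderate, is for an event that the subject cannot tolerate, that needs treating and that directly affects health. The top grade reads: "Severe: The adverse event endangers the subject's life, causing death or disability, and immediate emergency treatment is required".

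The SAP defines no other scale. SAP 7.2 uses moderate and severe as grade values when it fills in a missing severity.

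**The concern.** A treatment-emergent definition normally has two parts: new onset after exposure, and worsening after exposure of something already present. The second part of the SAP's definition sets the bar at reaching a particular grade instead of at any worsening, and that grade is the top one on the protocol's scale.

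Consider a mild catheter-site reaction that appears between consent and the flush, then becomes intolerable and needs treatment after the flush. It has gone from Mild to Moderate. It did not start after device use and it is not Severe, so under the literal rule it is not a TEAE. Worsening of a local reaction is one way in which flushing an indwelling line could do harm, so the group rates ought to capture it. What is at stake is the completeness of the TEAE and device-related TEAE tables.

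**Working it through.** The plan states no figure on this point, so the check sets the definition against the grading scale.

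**Inputs.** The TEAE rule and the content of the tables (SAP 6.4); three ordered grades, Mild, Moderate and Severe (Protocol 12.1.2); collection from consent (Protocol 12.1.4); screening of at most 3 days, possibly on the treatment day, and follow-up at 1 hour (Protocol 5.5.2).

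**Step 1: upward changes on the scale.** With three ordered grades there are 3 × 2 / 2 = 3 possible increases.

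| Grade before use | Grade at or after use | TEAE under the literal SAP 6.4 rule | TEAE if any worsening counts |
|---|---|---|---|
| Mild | Moderate | No | Yes |
| Mild | Severe | Yes | Yes |
| Moderate | Severe | Yes | Yes |

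The literal rule admits 2 of 3, and the reworded rule 3 of 3. This counts kinds of change and says nothing about how often each occurs.

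**Step 2: does the omitted change reach a table by another route?** The tables in SAP 6.4 count TEAEs. An event that keeps its pre-flush onset date meets neither part of the definition, so it appears only in the listing.

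**Step 3: does the data collection settle it?** Protocol 12.1.4 asks for the date of occurrence and the severity, but not for the date of a change in grade. Neither document says whether a worsened event is entered afresh or the existing entry is updated. A fresh entry dated after use qualifies under the onset route; an updated entry that moves from Mild to Moderate does not. Two sites could therefore count the same course of events differently.

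**Step 4: cases outside the grade count.** Worsening within a grade is not covered by the literal rule unless the event is Severe. An event already Severe before use that deteriorates further does not clearly *get* severe either. A rule that requires a one-grade increase would miss both cases, so the replacement should refer to any worsening.

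**Step 5: how often could this arise?** Onset must fall between consent and the flush. Exclusion criterion 3 (Protocol 5.2.2) removes patients with known redness, pain, phlebitis or infection at the insertion site before the trial, so the local-reaction example needs a reaction that first appears, or first becomes known, after eligibility review. It must then worsen within a follow-up whose only scheduled contact is at 1 hour. No adverse event rates are given, so an expected number cannot be calculated.

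**The case against.** The strongest objection is that this is a translation slip and not an analysis choice. The SAP is loose with these words. Its flowchart has severe adverse events where the protocol's has serious ones, and SAP 6.4 keeps the most serious of repeated events where severity grade seems to be meant. *Get severe* may simply stand for *get worse*. This stands as a caution about intent, and a reader should not infer that the sponsor chose to discard moderate worsening. It does not remove the need to change the text, because the sentence is the operative definition and severe is a defined grade in the protocol and a grade value in SAP 7.2.

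Three further points limit the consequence:

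- SAP 6.4 lists every adverse event, so nothing leaves the record. What can be lost is the contribution to the group rates.
- The eCRF and data management plan are separate documents (Protocol 8 and 8.3). If their rules enter a worsened event as a new record, it already counts. The omission is therefore conditional on recording practice that the protocol and SAP leave open.
- Safety is summarised descriptively (Protocol 6.4), and SAP 6.1 makes all comparisons other than the primary one exploratory. The same rule applies to both arms.

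A reader might infer that the safety endpoint is understated, or that the test device is favoured. The documents do not support either as a finding. The protocol's safety indicator is the incidence of adverse events and serious adverse events (Protocol 5.3.2), not of TEAEs. There are no rates from which to size a shortfall, and nothing suggests that the omission would differ between arms.

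**Conclusion.** The point holds as a defect in a definition. Taken literally, SAP 6.4 leaves mild-to-moderate worsening of a pre-existing event out of the TEAE and device-related TEAE tables, and no other section repairs this. The conclusion assumes that severe is programmed as the Protocol 12.1.2 grade and that a worsened event keeps its pre-flush onset. If the sponsor meant *worsen*, or if sites open a new record, the omission disappears, but neither is written down.

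The effect is probably small and cannot be quantified from the documents. It reaches the descriptive safety tables only; the primary non-inferiority test is unaffected. This is a minor correction, worth making because it is nearly free.

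**What to change.** In SAP 6.4, replace *get severe* with: worsen in severity (any increase, including by at least one grade of Protocol 12.1.2) at or after the start of device use.

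Add to the SAP and to the adverse event form instructions that a worsened event is entered as a new record with its own start time and grade. The flush start time is already recorded (Protocol 5.5.2), so the worsening can be dated against it and all sites will count it the same way.

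The cost is one SAP sentence and one form-completion note. The downside is a possibly slightly higher TEAE count.
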